*2) Telehealth Psychoeducation Sessions:* Caregivers in this group also attended two 90-minute sessions, but remotely via a video chat platform, rather than in-person. Otherwise, it followed the same format and PowerPoint materials as the in-person group. Sessions were still facilitated by a clinician, thereby maintaining the option to ask questions, discuss personalized examples, etc. This telehealth method of delivery allowed for more flexibility in scheduling, as sessions could be conducted on days when the MAC was not in-service, but required additional consideration for families who did not have a computer and Internet access. In these cases, a family was randomized to one of the other two psychoeducation groups.

*3) Psychoeducation as usual (PAU) - Informational Materials:* Caregivers in this group received basic paper psychoeducation resources, distributed at their feedback session. It was up to each caregiver how frequently and diligently they reviewed these resources, but they were encouraged to review them over the course of the following two weeks. These materials were intended to be akin to what a family might have access to at their pediatrician or primary care office, or perhaps on a website, if they were to look for ASD information on the Internet. To be consistent across study groups, the materials produced for these caregivers were comprehensive and included the same span of content as the PowerPoint slides used in the other two groups, but without structured sessions facilitated by a clinician. Upon distribution of materials, caregivers

were encouraged to reach out via phone or email if they had any questions, but only one caregiver did so.

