### Procedures

To track outcomes, caregivers completed a series of measures at five time points: (1) Time 1: intake, (2) Time 2: after feedback session, pre-psychoeducation, (3) Time 3: post-psychoeducation (i.e., after the second psychoeducation session or equivalent time after feedback for PAU group), (4) Time 4: at 6-week follow-up from the end of psychoeducation, and (5) Time 5: at 6-months follow-up from the end of psychoeducation. Times 1-4 consisted of measures of caregiver empowerment and ASD knowledge; Time 1 included measures of current services; Times 2-5 included a measure of new additional services since the prior timepoint; and Time 3 also included a measure of satisfaction with the psychoeducation services.

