### Measures

#### *Primary Outcome Measures*

Primary outcomes include the assessment of feasibility and satisfaction.

*Feasibility* of the study will be assessed by tracking the number of parents who completed the psychoeducation sessions and the attrition from Time 2 to Time 3.

*Caregiver satisfaction* with our psychoeducation services will be collected at Time 3 (the end of the final psychoeducation session or after two weeks of materials for the PAU group). This survey includes 32 questions on a 5-point Likert Scale from 0 (Completely Disagree) to 4 (Completely Agree). This measure surveys areas of convenience, process, quality, interpersonal sensitivity, satisfaction with psychoeducation, and general satisfaction. Because scales have varying numbers of items, each subscale is calculated by adding the item scores and dividing by the number of items in that scale, for a mean score ranging from 0 to 4. For the current study, we will sum 5 items related specifically to the psychoeducation services, for a possible total of 20. Higher mean scores indicate greater satisfaction.

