#### *Secondary Outcome Measures*

*Family Empowerment Scale* (FES; Koren et al., 1992) measures levels of perceived efficacy in areas such as community involvement and navigating services for the child and family. The FES is a 34-item questionnaire, providing a 5-point Likert scale for each item. The FES provides raw sums of the items within three domains of empowerment: Family (max = 60), Service System (max = 60), and Community/Political (max = 50). A higher raw score indicates greater empowerment in a given area. These factors are conceptually meaningful, congruence between them is high, and internal consistency is strong (.78-.89; Singh et al., 1995). In the current study, a sum total of all scales will be obtained, and a change score will be calculated between pre- and post-intervention. Positive scores indicate an increase in empowerment.

Caregivers also reported on their ASD knowledge and beliefs on the *Autism Stigma and Knowledge Questionnaire* (ASK-Q; Harrison et al., 2017). The ASK-Q consists of 49 True/False statements, which comprise four subscales of ASD knowledge: diagnosis, etiology, treatment,

and stigma, which results in a raw total score. The ASK-Q demonstrates strong internal consistency (.88). The knowledge subscales – diagnosis, etiology, and treatment – as well as the total score were used in this study. The items on this measure demonstrate strong face and construct validity, as well as cross-cultural utility. It also demonstrates strong discrimination between those who do and do not have adequate knowledge about ASD. In the current study, a sum total of all scales will be obtained, and a change score will be calculated between pre- and post-intervention. Positive scores indicate an increase in knowledge.

Parents will complete a *New Services Survey* to assess additional services they have received since the prior timepoint. In the current study, we will calculate the number of families in each condition (PE and PAU) that added any new service across all timepoints for the duration of the study up to 6 months post-psychoeducation.

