#### Statistical Analysis Plan

For Aim 1, the feasibility aim of this study, primary analyses will include tracking completion and attrition with the psychoeducation services across both groups: PE and PAU. These analyses will be descriptive only. Additionally, we will compare each group on satisfaction with the psychoeducation services. Independent t-tests will compare total satisfaction scores between the PE and PAU groups.

For the second aim, we will assess the differential efficacy across the PE and PAU conditions on the measures of caregiver empowerment and ASD knowledge, as well as new services received. First, we will calculate the change score (Time 3 minus Time 2) for the FES total score and the ASK-Q total score to determine the change in empowerment and knowledge from pre- to post-psychoeducation. Independent t-tests will compare the PE and PAU conditions on FES change score and on ASK-Q change score. To assess new services received, we will calculate the percent of families in each condition (PE and PAU) that indicated receiving a new service at any timepoint over the course of the study up to the 6-month follow-up. This analysis will be descriptive only.

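### The PE versus PAU new-services percentage counts the Time 2 survey, so a service gained before psychoeducation scores as an outcome of it

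*Combined protocol and SAP*

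**What the plan says.** - **When services are surveyed.** Procedures sets five timepoints. Time 1 (intake) records current services, and "Times 2-5 included a measure of new additional services since the prior timepoint". The second timepoint is defined as "Time 2: after feedback session, pre-psychoeducation".
- **When families are randomised.** The participants paragraph of the Protocol section places randomisation after the diagnostic feedback session. For the PAU arm the same section says: "Caregivers in this group received basic paper psychoeducation resources, distributed at their feedback session".
- **What is counted.** Secondary Outcome Measures counts the families in each condition that "added any new service across all timepoints for the duration of the study up to 6 months post-psychoeducation". The Statistical Analysis Plan turns this into the "percent of families in each condition (PE and PAU) that indicated receiving a new service at any timepoint over the course of the study", with the 6-month survey as the last. Neither section starts the count at Time 3.
- **What it is used for.** The second aim is to assess "differential efficacy across the PE and PAU conditions on the measures of caregiver empowerment and ASD knowledge, as well as new services received". The services analysis is described as descriptive only.
- **Where the other pre/post measures start.** The same paragraph of the Statistical Analysis Plan uses a "change score (Time 3 minus Time 2) for the FES total score and the ASK-Q total score". Feasibility, under Primary Outcome Measures, tracks "the attrition from Time 2 to Time 3".

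**The concern.** Each survey looks back to the previous timepoint, so the Time 2 survey covers intake to feedback. A service gained then cannot result from psychoeducation that had not begun, yet the counting rule scores it as a positive outcome in a comparison of the two conditions. New services is the only second-aim outcome handled this way; for empowerment and knowledge, Time 2 is the baseline.

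The literal rule also has an odd consequence. A family that reports a service at Time 2 and leaves before Time 3 is attrition under the first aim and a positive result under the second.

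At stake is how a descriptive percentage is read. The Brief Description says the results will guide a fully powered trial, and a difference that mixes services before and after psychoeducation is a poor guide to what psychoeducation does.

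**Working it through.** **Inputs from the documents.** The survey schedule, look-back window and position of Time 2 (Procedures); randomisation after feedback and a target of 21 children (Protocol); the counting rule (Secondary Outcome Measures and Statistical Analysis Plan). The plan states no rate, arm size or expected difference for this outcome, so there is no figure to reproduce.

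**Assumptions, not in the documents.** All 21 families are randomised, 11 to PE and 10 to PAU; 21 is the enrolment target, so it is an upper bound. The Times 3–5 rates are 70% in PE and 40% in PAU. The Time 2 rate *q* is 5% to 30%, equal in both arms and, to begin with, independent of later services.

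**Step 1: an exact identity.** Let *r* be the share of an arm with a new service at Time 2 and none at Times 3–5. Each arm's percentage as written is its Times 3–5 percentage plus *r*. Therefore

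difference as written − Times 3–5 difference = *r*(PE) − *r*(PAU).

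Each arm's percentage can only rise or stay the same; the difference can go either way. One Time 2-only family moves PE by 1/11 = 9.1 points or PAU by 1/10 = 10 points.

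**Step 2: expected shift and spread.** Under independence *r*(PE) = 0.3*q* and *r*(PAU) = 0.6*q*.

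- Expected number of Time 2-only families = 11 × 0.3*q* + 10 × 0.6*q* = 9.3*q*
- Chance of at least one = 1 − (1 − 0.3*q*)^11 × (1 − 0.6*q*)^10
- Mean shift = 0.3*q* − 0.6*q* = −0.3*q*
- SD of shift = √[*r*(PE)(1 − *r*(PE))/11 + *r*(PAU)(1 − *r*(PAU))/10]

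| *q* | Expected Time 2-only families | Chance of at least one | Mean shift (points) | SD (points) |
|---|---|---|---|---|
| 5% | 0.5 | 38% | −1.5 | 6.5 |
| 10% | 0.9 | 61% | −3 | 9.1 |
| 20% | 1.9 | 86% | −6 | 12.5 |
| 30% | 2.8 | 95% | −9 | 14.9 |

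**Step 3: direction in a single trial.** Exact binomial probabilities for the difference as written, relative to the Times 3–5 difference:

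| Split, *q* | Smaller | Unchanged | Larger |
|---|---|---|---|
| 11:10, 10% | 45% | 39% | 17% |
| 11:10, 20% | 66% | 14% | 20% |
| 12:9, 20% | 61.5% | 15.1% | 23.5% |

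If the later rate is 40% in both arms (11:10), the mean shift is 0 but its SD is 10.4 points at *q* = 10% and 14.2 points at *q* = 20%.

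**Step 4: without independence.** Let d0 be the PE effect on later services among families with no Time 2 service, and d1 the effect among families with one. In expectation the difference as written is (1 − *q*)d0, and the Times 3–5 difference is (1 − *q*)d0 + *q*d1, so the shift is −*q*d1. With d0 = 30 points and *q* = 20%, the difference as written is 0.8 × 30 = 24. The Times 3–5 difference is 30, 27, 24 or 22 for d1 = 30, 15, 0 or −10. Dilution therefore occurs only if PE also raises later services among families that already had one at Time 2.

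**Step 5: unequal Time 2 rates.** With the same 70% and 40% (a 30-point difference), *q* of 10% in PE and 30% in PAU gives (1 − 0.9 × 0.3) − (1 − 0.7 × 0.6) = 73% − 58% = 15 points. Reversing the two rates gives (1 − 0.7 × 0.3) − (1 − 0.9 × 0.6) = 79% − 46% = 33 points.

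**The case against.** The strongest reply is that whole-study counting looks deliberate. The Brief Description, Secondary Outcome Measures and the Statistical Analysis Plan all describe it, so the documents do not contradict each other on the count. That stands, and the count is a fair description of the programme. It does not make a service gained before psychoeducation evidence on PE versus PAU, which is the use the second aim gives it.

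Second, the effect is small beside ordinary sampling error. Under the same assumptions the Times 3–5 difference has an SD of √(0.7 × 0.3/11 + 0.4 × 0.6/10) = 20.8 points, against a mean shift of 1.5 to 6 points for *q* up to 20%. This stands, as does the fact that every rate is assumed: if no family has a Time 2-only service, nothing changes. Both keep the point minor.

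Third, PAU materials are handed out at feedback, so if the Time 2 survey is completed later, a Times 3–5 count could drop a few services gained after exposure, in PAU only. The length of any gap is not stated. The possibility is real, and a separate Time 2 row would show such services.

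Fourth, the plan does not say how families with no follow-up enter the denominator, so the attrition example rests on the literal any-timepoint wording. The gap is real, and it matters more once Time 2 is excluded.

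Finally, parts of the Protocol are in the past tense, so some data may already exist. That is a reason to label the change and keep the stated count, not to leave the comparison as it is.

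**Conclusion.** The concern holds, as a minor point. On the plain wording, the between-arm percentage includes a survey window that ends before psychoeducation and essentially before randomisation. That both percentages can rise and that the difference can shift in either direction follows from an identity and needs no assumption about rates.

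The size cannot be fixed from the documents. Under the illustrative 11:10 split and 70% versus 40%, the mean shift is less than one family's worth for a Time 2 rate of 20% or below, but the spread in a single trial is larger than the mean. No test, error rate or decision rule is affected, because the outcome is secondary and descriptive in at most about 21 families. What is affected is the reading of the percentage as a comparison of conditions.

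**What to change.** In Secondary Outcome Measures and the Statistical Analysis Plan:

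1. Define the between-arm outcome as any new service reported at Time 3, 4 or 5, and state how families missing those surveys enter the denominator.
2. Report Time 2 services by arm as a baseline descriptor beside the Time 1 current services.
3. Keep the whole-study count, labelled as a programme description. If data have already been examined, say that the restricted count was added afterwards.
4. State whether the Time 2 survey is completed before or after randomisation, and before or after PAU materials are handed out.

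The cost is wording in two sections and one extra table row; the survey is already taken separately at each timepoint. Reported percentages would be lower. Under the assumed 70% and 40%, PE and PAU fall by 1.5 and 3 points at a Time 2 rate of 5%, 3 and 6 at 10%, 6 and 12 at 20%, and 9 and 18 at 30%.

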### Brief Description

This study will be the pilot/feasibility phase of a future clinical trial. The proposed feasibility and pilot study aims to bridge the barriers to diagnosis by providing easy-to-access assessment for free, through a mobile unit that travels to rural locations and telehealth assessments. The diagnostic evaluation will confirm or rule out a diagnosis of ASD, followed by purposeful ASD psychoeducation for parents whose children are diagnosed.

Parents of children who meet criteria for a diagnosis of autism spectrum disorder (ASD) or are suspected to have ASD will be randomized into one of three groups (i.e., in-person psychoeducation, telehealth psychoeducation, or "psychoeducation as usual" with paper psychoeducation materials). Parents will complete outcome measures related to their satisfaction, empowerment, and autism spectrum disorder knowledge. Changes in empowerment and ASD knowledge from pre- to post-psychoeducation will be measured using t-tests. The investigators will also track if participants sought and/or received additional ASD-related services throughout the study, up to 6-months post-psychoeducation. Results from this study will help to guide a future, fully powered efficacy trial with a larger sample.

Added April 2020:

In light of the Virginia governor's stay-at-home order in response to the COVID-19 outbreak, which reached pandemic status approximately halfway through data collection, all in-person research and clinical services have been paused at Virginia Tech as of March 13, 2020. To continue to provide services to families in this time, in line with Executive Order 53 from the VA Governor to ensure that the stay-at-home orders do not limit the provision of health care or medical services, this study will begin exploring the feasibility of conducting tele-assessment, a comprehensive assessment battery via a secure video platform and phone.

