## Protocol

**Participants:** Participants will be recruited primarily from locales served by the Mount Rogers Community Services Board (MRCSB), including Smyth, Wythe, Bland, Carroll, and Grayson counties, and Galax City, in rural southwest Virginia, but we will also accept families from other local communities who contacted us to participate. We aim for 21 children between 2-15 years of age and one primary caregivers. Following a diagnostic feedback session, caregivers of children who receive an ASD diagnosis will be randomized to either attend psychoeducation sessions or receive comparable psychoeducation materials about ASD, with the goal of assessing feasibility and satisfaction of psychoeducation and of improving caregiver ASD knowledge and empowerment to seek and provide care for their child. Initially, families were going to be randomized to the following three psychoeducation conditions. Following the stay-at-home orders during the COVID-19 pandemic, however, we had to combine the first two conditions into one psychoeducation (PE) condition with clinician-led sessions. The psychoeducation as usual (PAU) condition, remained the same.

*1) In-person Psychoeducation Sessions:* Caregivers in this group attended two 90-minute, in-person psychoeducation sessions on our mobile autism clinic (MAC), in or near their hometown. During these sessions, a clinician presented a series of psychoeducation topics supplemented with PowerPoint slides. The first session covered signs/symptoms of ASD, risk factors associated with developing ASD (e.g., heritability, neurobiology, social motivation), and navigating the service systems (e.g., Individualized Education Program (IEP) process, insurance, and Medicaid waivers), while the second psychoeducation session covered evidence-based best practices and a basic introduction to behavior management principles. This delivery method allowed caregivers an opportunity to ask questions and receive immediate, live, and detailed answers from an expert clinician, to focus on specific examples relevant to their child.

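### The plan says it will track ASD-related services sought or received, but the outcome counts only receipt of any new service and can include services added before psychoeducation

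*Combined protocol and SAP*

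**What the plan says.** Four places bear on this outcome.

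- **Brief Description.** The investigators will "track if participants sought and/or received additional ASD-related services throughout the study, up to 6-months post-psychoeducation". This names two behaviours, seeking and receiving, and one type of service.
- **Protocol, Participants.** The goals of the psychoeducation comparison include "improving caregiver ASD knowledge and empowerment to seek and provide care for their child". The first session covers navigating service systems, with the IEP process, insurance and Medicaid waivers as examples.
- **Secondary Outcome Measures.** The New Services Survey is given "to assess additional services they have received since the prior timepoint". The outcome is the number of families in each condition "that added any new service across all timepoints for the duration of the study up to 6 months post-psychoeducation".
- **Statistical Analysis Plan.** The second aim assesses differential efficacy "on the measures of caregiver empowerment and ASD knowledge, as well as new services received". For services, the summary is the "percent of families in each condition (PE and PAU) that indicated receiving a new service at any timepoint", up to the 6-month follow-up. The plan adds: "This analysis will be descriptive only".

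The Procedures section places the survey at Times 2, 3, 4 and 5, each asking about the interval since the previous timepoint. It labels Time 2 as after feedback and before psychoeducation.

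**The concern.** The stated objective and the defined outcome differ in three ways: seeking is missing, the limit to ASD-related services is missing, and the counting window opens before the intervention.

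Seeking is the step closest to what the sessions teach. Waivers, insurance and the IEP process have to be started by the caregiver before anything can be received, and receipt then also needs an available provider or an approved application. With receipt alone, the pilot cannot tell a family that did not try from one that tried and is still waiting.

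This matters because the Brief Description says the results will guide a future, fully powered efficacy trial. Whether families sought services without obtaining them bears on the choice of outcome for that trial, and the present definition cannot show it.

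**Working it through.** The documents give no target, rate or power figure for this outcome, so there is no plan figure to reproduce. The check compares the text and adds two identities that show direction only.

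**1. Objective against definition**

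| Element | Brief Description | Secondary Outcome Measures | Statistical Analysis Plan |
|---|---|---|---|
| Seeking | included | not mentioned | not mentioned |
| Receipt | included | included | included |
| Type of service | ASD-related | any new service | a new service |
| End of window | 6 months after psychoeducation | same | 6-month follow-up |
| Start of window | throughout the study | across all timepoints | any timepoint |

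Receipt and the end of the window agree. Seeking and the type of service do not carry through. No section defines a referral, application, contact or waiting-list item.

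**2. Whether another measure covers seeking**

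The FES "measures levels of perceived efficacy in areas such as community involvement and navigating services for the child and family". That is perceived efficacy, not what the caregiver did. The Procedures section collects empowerment at Times 1-4 only, so there is no FES at 6 months. The Statistical Analysis Plan uses only its change from Time 2 to Time 3. The FES therefore does not record seeking, and its analysis stops at the end of psychoeducation.

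**3. What a receipt-only count does**

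Let *s* be the proportion of families in an arm that seek a service and *a* the proportion of seekers who receive it within follow-up.

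- Receipt in an arm = *s* × *a*.
- With the same *a* in both arms, the difference in receipt = *a* × (*s*_PE − *s*_PAU).

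Since *a* is at most 1, limited availability shrinks the difference between arms. It does not create or reverse one. The documents give neither *s* nor *a*, so the amount of shrinkage is unknown.

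**4. What the Time 2 survey does**

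The survey is given at Times 2, 3, 4 and 5, which is four administrations. Time 2 looks back to intake (Time 1) and is labelled pre-psychoeducation, so one of the four covers an interval before the intervention.

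Let *q* be the proportion already positive at Time 2, equal in both arms, and *p* the proportion adding a service at Times 3-5, assumed unrelated to Time 2 status.

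- Percent positive at any timepoint = *q* + (1 − *q*) × *p*.
- Difference between arms = (1 − *q*) × (*p*_PE − *p*_PAU).

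Families positive at Time 2 count as positive whatever happens later. This again dilutes a difference, by an amount the documents do not allow one to compute. Counting Times 3-5 only removes it. Those three surveys still cover the whole interval from Time 2 to 6 months, because each asks about the time since the one before.

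**The case against.** The strongest reply is that receipt is a legitimate and harder endpoint, that the Brief Description is only a summary and says and/or, and that the Procedures, Secondary Outcome Measures and Statistical Analysis Plan sections agree with one another on new or received services. Empowerment has its own instrument, and services are listed beside it, not as a proxy for it. The outcome is secondary and descriptive, in a pilot that calls its second aim significantly underpowered. The survey form is not reproduced, so it may already be limited to ASD-related services or record more than its one-sentence description.

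Most of this stands as a limit on severity. Reporting receipt is consistent with the objective but incomplete, because half of what the plan says it will track has no stated measure. If the form does hold the missing items, the definitions should say so and the analysis should use them.

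A reader might go further in three ways that the documents do not support.

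- *The outcome reflects local supply more than empowerment.* That ranking needs data on access or waiting times, and there are none. With equal access in randomised arms, supply dilutes a difference.
- *The loss can be put in percentage points.* Any such figure would only restate assumed seeking and access rates.
- *A null result would be misread as no effect on help-seeking.* No test is planned for services, and the plan does not present the percentage as a measure of help-seeking.

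On timing, much of the Protocol and Procedures text is in the past tense, which suggests that many surveys may already have been returned. This limits what the fix can recover, so a fallback is given.

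**Conclusion.** The mismatch holds on the text alone. Of the two behaviours in the stated objective, seeking has no measure or analysis. The limit to ASD-related services is absent from both outcome definitions. One of the four surveys feeding the arm comparison precedes psychoeducation.

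No numerical size follows from the documents. The direction, dilution of a difference between arms, rests on two assumptions: access and Time 2 positivity are equal in the two arms, and later additions are unrelated to Time 2 status. The first is reasonable under randomisation within each phase of the study. It is less secure for the pooled arms if availability changed when the design went from three arms to two, since the documents state neither the allocation ratio nor anything about availability.

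This is a moderate point, worth correcting because the change is small and lets the pilot answer a question it sets itself. It invalidates no planned test.

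**What to change.** **Survey.** On the New Services Survey at Times 3-5, add two entries for each new service: whether it is ASD-related, and its status (sought, applied for or wait-listed; or received).

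**Secondary Outcome Measures and Statistical Analysis Plan.** Report descriptively, by arm, over Times 3-5:

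1. the percent of families that sought or received an ASD-related service;
2. the percent that received one.

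Keep the current figure, any new service at any timepoint, as a supplement. State that receipt also depends on availability.

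**Cost.** One status field, one tick per service, and an additional descriptive row. The form is slightly longer. Seeking is self-reported by caregivers who know which format they received, so it is softer than receipt. For surveys already returned, status will be missing or must be asked retrospectively at the next contact; report how many families that affects in each arm.

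**If the form can no longer be changed.** Restrict the count to ASD-related services at Times 3-5, remove seeking from the objective in the Brief Description, and state that receipt depends on availability as well as on what the caregiver did. This needs no new data if the returned surveys identify the service, but leaves seeking unmeasured.
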